13.6 Statistical Hypotheses

All analyses are superiority framework; the null hypotheses are that there is no difference in outcome rates between participants who do / do not receive immunoreduction. The alternative hypotheses for both safety and efficacy outcomes is that the outcome occurs more frequently in the immunoreduction group.

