2.1 Hypotheses

Kidney and liver transplant recipients who had a negative or low (≤ 2500 U/mL) anti-SARS-CoV-2 S response (using the Roche Elecsys® assay) to a completed primary series of the Moderna COVID-19 Vaccine or the Pfizer-BioNTech COVID-19 Vaccine will develop an enhanced SARS-CoV-2 antibody response after receiving a dose of study vaccine, with or without reduction of their maintenance transplant immunosuppression regimen.

Temporary reduction of maintenance immunosuppression as directed in this protocol will result in higher fold increase in antibody titer than achieved in those who do not have IS reduction, without an increased risk of alloimmune events (rejection or development of dnDSA).

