13.2 Endpoints/Outcomes

The primary endpoint is the proportional increase in antibody titer U/mL (using the Roche Elecsys® anti-RBD assay) at 30 days after the study dose of vaccine. Negative or very low antibody responses (<10 U/mL) will be imputed to 10 U/mL, to reduce the influence of measurement error on the proportional increase calculation among individuals with very low titers. Secondary safety endpoints include: local and systemic vaccine reactogenicity and/or allergy; serious adverse events occurring during the 30 days following the additional COVID-19 vaccine dose; treated acute cell-mediated and/or antibody-mediated allograft rejection (clinical or biopsy-proven) within 60 days following the COVID-19 vaccine dose; development of de novo donor-specific anti-HLA antibody within 90 days of the vaccine; graft loss within 60 days of the vaccine; and death within 60 days of the vaccine. Secondary efficacy endpoints include: SARS-CoV-2 PCR positivity; symptomatic COVID-19; COVID-19 requiring hospitalization; and longitudinal changes in SARS-CoV-2 antibody response during the study.

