13.4.2 Primary Analysis of Primary Endpoint(s)/Outcome(s)

The primary endpoint is a continuous measurement. All individuals whose primary endpoint is measured will be included in the analysis population.

For the comparison of immunoreduction vs no immunoreduction, we will reject the null hypothesis if the two-sided rank-sum p value comparing the -fold increase between the two groups falls below 0.05.

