13.4.3 Analyses of Secondary and Other Endpoint(s)/Outcome(s)

All binary secondary endpoints will be analyzed using a Fisher exact test. Severe adverse events will be analyzed by calculating the incidence rate difference with a two-sided 95% confidence interval for immunoreduction vs no immunoreduction participants.

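### Section 13.6 gives one direction of effect for every outcome, which is the harm direction for the COVID-19 endpoints, and its superiority framework cannot support the claim of no added alloimmune risk

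*Combined protocol and SAP*

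**What the plan says.** Section 13.6 sets the inferential frame for the whole trial: "All analyses are superiority framework; the null hypotheses are that there is no difference in outcome rates". It then gives a single alternative: "The alternative hypotheses for both safety and efficacy outcomes is that the outcome occurs more frequently in the immunoreduction group".

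Section 13.2 names the endpoints this covers: "Secondary efficacy endpoints include: SARS-CoV-2 PCR positivity; symptomatic COVID-19; COVID-19 requiring hospitalization". The one remaining efficacy endpoint there, longitudinal antibody change, is not binary. On testing, Section 13.4.3 says "All binary secondary endpoints will be analyzed using a Fisher exact test", with no sidedness and no alpha. The only interval planned for a secondary endpoint is in the same section: "Severe adverse events will be analyzed by calculating the incidence rate difference with a two-sided 95% confidence interval".

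The plan uses both conventions elsewhere. The primary test (13.4.2) is decided on "the two-sided rank-sum p value", while the interim dnDSA comparison (13.5.2) is explicitly a one-sided Fisher test.

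Section 2.1 hypothesizes that immunosuppression (IS) reduction "will result in higher fold increase in antibody titer than achieved in those who do not have IS reduction", and that it will do so "without an increased risk of alloimmune events (rejection or development of dnDSA". No non-inferiority margin or acceptable excess risk for rejection or dnDSA is stated anywhere.

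**The concern.** There are two separate problems.

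**Direction.** The three binary efficacy endpoints are bad outcomes, so benefit means fewer of them. An alternative of more events with reduction is the harm direction. Because 13.4.3 is silent on sidedness, 13.6 is the only text on direction that an analyst could consult for these tests.

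**The safety hypothesis.** Failing to reject a null of no difference does not show that risk is not increased. That needs an interval judged against a tolerable excess, or a stated margin. The plan has neither for rejection, dnDSA, graft loss or death. Whether a short IS reduction is safe for the graft is half of the Section 2.1 hypothesis, and Section 1.3 describes it as unknown.

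**Working it through.** **Inputs**
- 200 participants per arm (13.7).
- Expected rejections: 5-6 over the study (11.5). Assuming these refer to all 400 participants, 5/400 = 1.25% and 6/400 = 1.5%.
- The rejection endpoint covers 60 days (3.3.1), so its rate may be lower than this whole-study figure.
- Scheduled DSA testing after vaccination is in kidney recipients only (Appendices 2 and 3), so dnDSA has fewer than 200 per arm if liver recipients enrol.
- The documents give no COVID-19 event rate; the rates and counts below are assumptions.

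The plan gives no power or precision figure for any secondary endpoint, so there is none to reproduce.

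**1. Direction.** Fisher's exact test on assumed counts of 20/200 with reduction versus 40/200 without:

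| Alternative | p |
|---|---|
| More events with reduction (as 13.6 reads) | 0.998 |
| Two-sided | 0.007 |

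The table below gives the probability of p < 0.05 if reduction halves the control rate:

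| Assumed control rate | One-sided as 13.6 reads | Two-sided |
|---|---|---|
| 10% | under 0.01% | 41% |
| 20% | under 0.01% | 77% |
| 30% | under 0.01% | 94% |

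The sidedness decision therefore settles whether a benefit could be seen at all.

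**2. Power to see an excess of rejection.** With X1 ~ Bin(200, k·p0) for reduction and X0 ~ Bin(200, p0) for control, power is the sum of P(X1 = i)·P(X0 = j) over all (i, j) with Fisher p < 0.05.

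| True risk ratio k | Two-sided power, p0 = 1.25% to 1.5% | One-sided 0.05 |
|---|---|---|
| 2 | 7% to 9% | 12% to 15% |
| 3 | 24% to 31% | 35% to 43% |
| 4 | 48% to 58% | 61% to 71% |
| 5 | 70% to 80% | 80% to 88% |

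With 3 control events (3/200 = 1.5%), two-sided significance needs 12 in the reduction arm. An observed 9 versus 3, a threefold excess, gives p = 0.14.

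**3. What equal counts would show.** For 3/200 the Wilson 95% limits are l = 0.51% and u = 4.32%. The Newcombe limits for the difference between 3/200 and 3/200 are ±√[(1.50 − 0.51)² + (4.32 − 1.50)²] = ±√(0.98 + 7.95) ≈ ±3.0 points. The upper limit of +3.0 on a 1.5% control rate corresponds to 4.5%, three times that rate.

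**4. What a margin would need.** With equal true rates p, one-sided 0.025 and 80% power, n per arm = (1.96 + 0.842)²·2p(1 − p)/margin². For an assumed 3-point margin:
- p = 1.25%: 7.85 × 0.02469/0.0009, giving 216.
- p = 1.5%: 7.85 × 0.02955/0.0009, giving 258.

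An assumed 2-point margin needs 485 to 580. With 200 per arm, only margins somewhat above 3 points are reachable at 80% power.

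**The case against.** **13.6 need not set sidedness.** The primary test also falls under 13.6 and has a directional hypothesis in 2.1, yet it is two-sided. Where the plan wants a one-sided test, in 13.5.2, it says so. Naming an expected direction and testing two-sided is ordinary practice. This stands. A reader might infer that a reduction in COVID-19 could never be declared, but that holds only if the Fisher tests are one-sided as worded, and no section says they are.

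**No rule equates non-significance with safety.** The formal objective in 2.3 is to determine incidence, which is estimation. This also stands: a reader might infer that a null Fisher result will be reported as no added risk, but the plan does not say so. The gap is that 2.1 makes the claim and nothing in Section 13 could support it.

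**Large rises would not all be missed.** A reader might infer that any several-fold increase in rejection would usually go undetected. That is too broad: two-sided power is about one half at fourfold and 70-80% at fivefold.

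**There are other safeguards.** The pausing rules in 11.5, applied by regimen and keyed to three times the expected rate, and the two interim dnDSA comparisons in 13.5.2 protect participants during the trial. They do not estimate the final between-arm difference, so they do not fill the gap.

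**Conclusion.** The point holds in two limited parts.

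- **Direction.** The sentence in 13.6 is wrong for three secondary endpoints, and the sidedness of their tests is unstated. If the tests are two-sided, this is an error of wording with no effect on p values. If they are one-sided as worded, a benefit could not be detected. The choice should be fixed before data are seen, particularly in an open-label trial.
- **Alloimmune risk.** The analysis as planned cannot support the no-increased-risk hypothesis in 2.1. At the protocol's own background rate a doubling or tripling of rejection would usually be non-significant, and equal counts would still be compatible with a threefold rate.

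The power figures rest on 5-6 events among 400, equal arms of 200 and no dropout. A lower 60-day rate would reduce power further, as would fewer participants analysed; no dnDSA rate is given, so no figure is offered for it. The primary analysis is two-sided and unaffected. The matter should be fixed, but because it touches only secondary endpoints it does not threaten the main result.

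**What to change.** 1. In 13.6 and 13.4.3, state that the final tests of binary endpoints are two-sided, with the alpha. State that for PCR positivity, symptomatic COVID-19 and COVID-19 hospitalization, benefit means fewer events in the reduction arm.
2. In 13.4.3, add the risk difference with a two-sided 95% confidence interval for rejection, graft loss, death and dnDSA, with dnDSA restricted to kidney recipients, where it is measured.
3. State that a non-significant Fisher test will not be taken as evidence of no increased risk. Either judge the 2.1 safety statement from the confidence interval, naming beforehand the excess that would be tolerable, or reword it as estimation. Rewording is the more realistic choice unless an excess above about 3 points is acceptable.

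The cost is text only: no extra participants, visits or samples, and no change to the primary analysis. The downside is a more cautious safety conclusion.

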13.7 Sample Size Considerations

Comparison of the primary endpoint will use a two-sided ranksum test. There will be 400 patients, 200 per treatment group. Power calculations assume an α of 0.05. The power of the study will depend on the distribution of -fold changes in each group.

We ran simulations in which -fold changes are log-normally distributed, and computed power based on the ratio of -fold change between the two groups. For example, if the average -fold increase in one group is a twofold increase and in the other group, a threefold increase, the ratio of -fold change is $3/2$ or 1.5. (This does not mean that each individual in one group experienced a twofold increase; some individuals would experience a greater increase, and some a smaller increase.) In the simulation, with an N of 400, generally the study has 80% power to detect a difference of 20% (e.g. mean 2.5-fold increase in one group vs 3-fold increase in the other.)

14. Identification and Access to Source Data**14.1 Source Data**

Source documents and source data are the original documentation where subject information, visits consultations, examinations and other information are recorded. Documentation of source data is necessary for the reconstruction, evaluation and validation of clinical findings, observations, and other activities during a clinical trial.

14.2 Access to Source Data

The site investigators and site staff will make all source data available to the DAIT/NIAID and their representatives as well as to relevant health authorities (Food and Drug Administration). Authorized representatives as noted above are bound to maintain the strict confidentiality of medical and research information that may be linked to identified individuals.

15. Quality Assurance and Quality Control

Quality control (QC) procedures will be implemented beginning with the data entry system and data QC checks. Any missing data or data anomalies will be communicated to the site for clarification/resolution.

Following written Standard Operating Procedures (SOPs), the monitors will verify that the clinical trial is conducted, data are generated, and biological specimens are collected, documented (recorded), and reported in compliance with the protocol, International Conference on Harmonisation Good Clinical Practice (ICH GCP), and applicable regulatory requirements.

The investigational site will provide direct access to all trial related sites, source data/documents, and reports for the purpose of monitoring and auditing by the sponsor, and inspection by local and regulatory authorities.

16. Protocol Deviations

16.1 Protocol Deviation Definitions

Protocol Deviation – The investigators and site staff will conduct the study in accordance with the protocol; no deviations from the protocol are permitted. Any change, divergence, or departure from the study design or procedures constitutes a protocol deviation. As a result of any deviation, corrective actions will be developed by the site and implemented promptly.

Major Protocol Deviation (Protocol Violation) - A Protocol Violation is a deviation from the IRB approved protocol that may affect the subject's rights, safety, or well-being and/or the completeness, accuracy and reliability of the study data. In addition, protocol violations include willful or knowing breaches of human subject protection regulations, or policies, any action that is inconsistent with the NIH Human Research Protection Program's research, medical, and ethical principles, and a serious or continuing noncompliance with federal, state, local or institutional human subject protection regulations, policies, or procedures.

Non-Major Protocol Deviation - A non-major protocol deviation is any change, divergence, or departure from the study design or procedures of a research protocol that does not have a major impact on the subject's rights, safety or well-being, or the completeness, accuracy, and reliability of the study data.

16.2 Reporting and Managing Protocol Deviations

The study site principal investigator has the responsibility to identify, document and report protocol deviations as directed by the study Sponsor. However, protocol deviations may also be identified during site monitoring visits or during other forms of study conduct review.

17. Ethical Considerations and Compliance with Good Clinical Practice

17.1 Statement of Compliance

This clinical study will be conducted using good clinical practice (GCP), as delineated in *Guidance for Industry: E6 Good Clinical Practice Consolidated Guidance*, and according to the criteria specified in this study protocol. Before study initiation, the protocol and the informed consent documents will be reviewed and approved by the Sponsor and Institutional Review Board (IRB). Any amendments to the protocol or to the consent materials will also be approved by the Sponsor and IRB before they are implemented.

17.2 Informed Consent Process

The consent process will provide information about the study to a prospective participant and will allow adequate time for review and discussion prior to his/her decision. The principal investigator or designee listed on the Investigator of Record Agreement will review the consent and answer questions. The prospective participant will be told that being in the trial is voluntary and that he or she may withdraw from the study at any time, for any reason. All participants will read, sign, and date a consent form before undergoing any study procedures. Consent materials will be presented in the participants' primary language. A copy of the signed consent form will be given to the participant.

The consent process will be ongoing, and any new findings will be communicated to the participants. The consent form will be revised when important new safety information is available, the protocol is amended, and/or new information becomes available that may affect participation in the study.

Appendix 1: Screening (All Participants)

Initial Screening Assessment

• Chart review• Antibody consent• Anti-SARS-CoV-2 S (Roche Assay)
Final Screen

• Study consent form• Serum creatinine, eGFR (Kidney)• DSA (kidney only, sent to central lab, 90 day window)• Research blood (sent to central lab)• Hepatic panel, INR, direct bilirubin (liver)• Tacrolimus trough level• Pregnancy test (women of childbearing potential)
Randomization

1) Once the participant meets full eligibility, the participant may be randomized2) Once the participant is randomized, the appropriate appendix should be followed based on the group assignment:
○ Appendix 2: COVID-19 Vaccine Dose Alone 
OR
 
○ Appendix 3: IS Reduction plus COVID-19 Vaccine Dose

Appendix 2: Schedule of Events (COVID-19 Vaccine Dose Alone)

Study Schedule	Days		Weeks						Months				
Time points	0	3 ¹	1	2	3	4	5	6	3	6	9	12	For Cause ²
Visit #	01	02	03	04	05	06	07	08	09	10	11	12	FC
Visit Windows (+/-)	-	1d	1d	3d	3d	3d	3d	3d	2w	2w	2w	2w	-
General Assessments													
Study Contact ³	X		X	X	X	X	X	X	X	X		X	X
Medications (immunosuppression, PrEP, COVID-19 treatment)	X ⁴	→	→	→	→	→	→	→	X	X ⁵	X ⁵	X ⁵	X
Assessment of Events (AE, SAE, rejection, graft loss)	X	→	→	→	→	→	→	→	→	→	→	X	X
Clinical Laboratory Assessments													
Complete Blood Count with differential	X			X		X			X	X		X	
Metabolic Panel ⁶	X								X	X		X	
eGFR, serum creatinine (kidney)	X		X	X	X	X	X	X					
Hepatic Panel including direct bilirubin (liver)	X									X			
Quantitative Immunoglobulins	X									X			
SARS-CoV-2 PCR (nasal swab, clinical)	X ⁷					X			X	X	X	X	X
Investigational Intervention													
COVID-19 mRNA Vaccine	X												
Central Laboratory Assessments													
SARS-CoV-2 PCR (nasal swab, research)	X					X			X	X		X	X
Oral fluid anti-N and anti-S immunoglobulin levels	X					X			X	X		X	X
Anti-SARS-CoV-2 S (Roche Elecsys®)				X		X			X	X		X	X
Donor Specific Antibodies (kidney only)						X			X	X		X	X
Antibody/Neutralization assays	X			X		X			X	X		X	X
Spike Protein (subset of sites)	X	X											
Proteomics	X	X ⁸				X							
Transcriptomics	X	X ⁷				X							
T and B Cell Assays	X			X		X			X	X		X	X

¹ May be a home draw. The spike protein will only be performed at a subset of clinical sites.

² Unscheduled "for cause" visit for suspected rejection. Participants with confirmed COVID-19 will send in a nasal swab for research.

³ Study contacts may be remote.

⁴ Ensure the participant has not taken any medications since screening that would make them ineligible.

⁵ Only PrEP and COVID-19 related treatment collected at these visits.

⁶ Comprehensive metabolic panel at baseline, basic metabolic panel all other timepoints (see study definitions).

⁷ If the Day 0 nasal swab is positive, the participant will be prematurely discontinued and followed until Day 30 for safety. This includes the Day 30 clinical labs, DSA and AE/SAE assessment. No further mechanistic blood will be collected.

⁸ These Day 3 assessments will only be collected on participants included in the Day 3 spike protein.

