3.3 Secondary Endpoints

3.3.1 Secondary Safety Endpoints

Local and systemic vaccine reactogenicity and/or allergy
Serious adverse events occurring during the 30 days following the additional dose of vaccine
Treated acute cell-mediated and/or antibody-mediated allograft rejection (clinical or biopsy-proven) within 60 days following the additional dose of vaccine
Development of de novo donor-specific anti-HLA antibody within 90 days of the vaccine
Graft loss within 60 days of the vaccine
Death within 60 days of the vaccine

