5.3 Risks Associated with IS Reduction

Any decrease in dose or frequency of immunosuppressive medications in a transplant recipient carries the risk of alloimmune activation leading to acute cellular rejection, subclinical rejection, acute or chronic antibody-mediated rejection, and/or the formation of de novo DSA. The inclusion criteria and the specific immunomodulatory strategies have been designed to minimize, but do not eliminate, this risk. Study participants undergoing IS reduction will be closely monitored for evidence of graft injury and will be returned to their baseline immunosuppressive regimen should graft injury be evident. In addition, subjects will be monitored for the development of de novo DSA throughout the study period.

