8.3.2 Vaccination Visit: Day 0 (All Participants)

All participants will be scheduled for a vaccination visit.

Participants will have baseline research blood, oral fluid, and nasal samples collected on Day 0 per the Schedule of Events (Appendix 2 (COVID-19 Vaccine Dose Alone) and Appendix 3 (IS Reduction plus COVID-19 Vaccine Dose)). Following sample collection, the participant will proceed to the administration location and receive the assigned dose of COVID-19 vaccine (see [Section 6](#) for vaccine details).

Participants will be observed for 30 minutes post vaccine administration.

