12.4 Collection and Recording of Adverse Events

12.4.1 Collection Period

Adverse Events temporally associated (24 hours) with the research blood draws and nasal swabs will be collected from the time of the screening visit until a subject completes study participation.

COVID-19 Vaccine Dose Alone: Adverse Events as defined in Section 12.2.1 will be collected for 30 days following COVID-19 vaccine administration. Serious Adverse Events will be collected for 6 months following vaccine administration.

COVID-19 Vaccine Dose plus IS Reduction: All Adverse Events will be collected in those who undergo immunosuppression reduction occurring from the onset of IS reduction until 30 days after return to full immunosuppression. Serious Adverse Events will be collected for 6 months post onset of IS reduction.

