Appendix 3: Schedule of Events (IS Reduction plus COVID-19 Vaccine Dose)

Study Schedule	Days			Weeks						Months				
Time points	-5	0	3 ¹	1	2	3	4	5	6	3	6	9	12	For Cause ²
Visit #	01	02	03	04	05	06	07	08	09	10	11	12	13	FC
Visit Windows (+/-)	-	-	1d	1d	3d	3d	3d	3d	3d	2w	2w	2w	2w	-
General Assessments														
Study Contact ³	X	X		X	X	X	X	X	X	X	X		X	X
Medications (immunosuppression, PrEP, COVID-19 treatment)	X ⁴	→	→	→	→	→	→	→	→	X	X ⁵	X ⁵	X ⁵	X
Assessment of Events (AE, SAE, rejection, graft loss)	X	→	→	→	→	→	→	→	→	→	→	→	X	X
Clinical Laboratory Assessments														
Complete Blood Count with differential		X			X		X				X	X		X
Metabolic Panel ⁶		X								X	X			X
eGFR, serum creatinine (kidney)		X		X	X	X	X	X	X					
Hepatic Panel including direct bilirubin (liver)		X									X			
Quantitative Immunoglobulins		X									X			
SARS-CoV-2 PCR (nasal swab, clinical)		X ⁷					X			X	X	X	X	X
Investigational Intervention														
Immunosuppression Reduction	X	→	→	→	X ⁸									
COVID-19 mRNA Vaccine		X												
Central Laboratory Assessments														
SARS-CoV-2 PCR (nasal swab, research)		X					X			X	X		X	X
Oral fluid anti-N and anti-S immunoglobulin levels		X					X			X	X		X	X
Anti-SARS-CoV-2 S (Roche Elecsys [®])					X		X			X	X		X	X
Donor Specific Antibodies (kidney only)							X			X	X		X	
Antibody/Neutralization assays		X			X		X			X	X		X	X
Spike Protein (subset of sites)		X	X											
Proteomics		X	X ⁹				X							
Transcriptomics		X	X ⁸				X							
T and B Cell Assays		X			X		X			X	X		X	X

¹ May be a home draw. The spike protein will only be performed at a subset of clinical sites.² Unscheduled "for cause" visit for suspected rejection. Participants with confirmed COVID-19 will send in a nasal swab for research.³ Study contacts may be remote.⁴ Ensure the participant has not taken any medications since screening that would make them ineligible.⁵ Only PrEP and COVID-19 related treatment collected at these visits.⁶ Comprehensive metabolic panel at baseline, basic metabolic panel all other timepoints (see study definitions).⁷ If the Day 0 nasal swab is positive, IS reduction will be prematurely discontinued and participants will be followed until Day 30 for safety. This includes the Day 30 clinical labs, DSA and AE/SAE assessment. No further mechanistic blood will be collected.⁸ Participant will be informed to restart full IS the following day.⁹ These Day 3 assessments will only be collected on participants included in the Day 3 spike protein.

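### Footnote 7 stops follow-up of randomised, swab-positive participants at Day 30, short of the plan's own 60- and 90-day safety endpoints

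*Combined protocol and SAP*

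**What the plan says.** Randomisation follows screening (Appendix 1), and IS reduction starts at Day -5 (Appendix 3). The clinical PCR swab is taken on Day 0. Section 8.3.2 then reads: "Following sample collection, the participant will proceed to the administration location and receive the assigned dose of COVID-19 vaccine". It mentions no wait for the PCR result.

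Footnote 7 governs a positive swab:

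- Appendix 2 (vaccine alone): "the participant will be prematurely discontinued and followed until Day 30 for safety".
- Appendix 3 (IS reduction): "IS reduction will be prematurely discontinued and participants will be followed until Day 30 for safety".
- Both then list what is kept and what stops: "This includes the Day 30 clinical labs, DSA and AE/SAE assessment. No further mechanistic blood will be collected".

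Section 3.3.1 sets longer safety windows. One endpoint is treated "allograft rejection (clinical or biopsy-proven) within 60 days following the additional dose of vaccine"; graft loss and death also run to 60 days. Another is "Development of de novo donor-specific anti-HLA antibody within 90 days of the vaccine". Section 5.3 offers as a safeguard for IS reduction that "subjects will be monitored for the development of de novo DSA throughout the study period".

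Two general rules carry no exception for a positive swab. Section 11.1 follows everyone for 12 months. Section 12.4.1 states for the vaccine-alone arm that "Serious Adverse Events will be collected for 6 months following vaccine administration", and for the reduction arm it collects serious adverse events (SAEs) for six months from the start of reduction.

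**The concern.** A swab result obtained after randomisation decides how long a participant's safety is observed, and the stopping point lies inside the endpoint windows. The trial asks whether IS reduction around vaccination brings alloimmune harm. A vaccinated reduction-arm participant with a positive swab has had some days of reduced immunosuppression and an infection, and is then observed for only half of the rejection window.

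The wording also differs by arm. One footnote discontinues the person and the other discontinues the reduction. Sites could reasonably do different things in the two arms of an open-label comparison. Sections 11.1 and 12.4.1 tell them something different again.

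**Working it through.** **Step 1: who is affected.** The 60- and 90-day endpoints run from the vaccine dose, so the endpoint gap exists only for swab-positive participants who received it. Section 8.3.2 does not say whether the result is known by then.

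**Step 2: windows against the Day 30 stop** (six months taken as 183 days).

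| Item | Source | Planned | Not observed under footnote 7 |
|---|---|---|---|
| SAE endpoint | 3.3.1 | 30 days | none |
| Treated rejection, graft loss, death | 3.3.1 | 60 days | 60 - 30 = 30 of 60 days (50%) |
| De novo DSA (kidney) | 3.3.1, Appendices 2 and 3 | 90 days; draws at Week 4 and Month 3 | 1 of 2 draws (Month 3) |
| SAEs, vaccine alone | 12.4.1 | 183 days from vaccine | 183 - 30 = 153 days (84%) |
| SAEs, IS reduction | 12.4.1 | 183 days from Day -5 | 183 - 35 = 148 days (81%) |

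Two of these rows need qualifying. Section 12.2.1 counts reduction-arm SAEs to six months after return to full immunosuppression. If that return is at about Day 0, the last row becomes about 153 days rather than 148. The Month 3 visit has a window of two weeks either side (Section 8.7), about Days 76-104, so that draw can fall after Day 90 in any participant.

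**Step 3: does other text close the gap?**

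- Section 11.2 does not list a positive swab among its reasons for termination.
- Section 11.4 makes a final visit after withdrawal optional.
- Section 12.4.3 follows events already recorded. It does not look for new ones after Day 30.
- Sections 11.1 and 12.4.1 would close the gap if they prevailed, but a specific footnote is likely to be read as overriding them.

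**Step 4: number affected (assumption).** The documents give no Day 0 positivity. At 1-5% of 400, the number is 4-20. This is an upper count if some of them are not vaccinated.

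**Step 5: expected events unseen in Days 31-60.** Section 11.5 expects 5-6 rejections, 6-7 graft losses and about 5 deaths in the study. Spread evenly over 365 days (assumption), unseen events = number affected x events / 400 x 30/365:

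- Rejections: 4 x 5/400 x 30/365 = 0.004, to 20 x 6/400 x 30/365 = 0.025.
- Graft losses: 4 x 6/400 x 30/365 = 0.005, to 20 x 7/400 x 30/365 = 0.029.
- Deaths: 4 x 5/400 x 30/365 = 0.004, to 20 x 5/400 x 30/365 = 0.021.
- Sum of the unrounded values: 0.013 to 0.074.

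As a pessimistic case for rejection, suppose every event falls within 60 days and half fall after Day 30. The figures are then 4 x 5/400 x 0.5 = 0.025 and 20 x 6/400 x 0.5 = 0.15. All these figures use the background counts of Section 11.5, without any added risk from IS reduction or infection.

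**Step 6: the Week 4 titre, if it were not drawn.** Section 13.7 states 80% power at N = 400 but gives no standard deviation, so that figure cannot be reproduced independently. Taking it as given, power = Phi(2.8016 x sqrt(N/400) - 1.96). This gives 79.6% at N = 396 and 78.0% at N = 380.

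**The case against.** The strongest reply is that almost nothing is lost. The expected unseen events are a small fraction of one event, and every headcount rests on an assumed positivity. That stands. A reader might infer that the safety results or the pausing counts of Section 11.5 are distorted, but nothing in the documents supports this.

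Next, Day 30 has a basis in the plan. It matches the 30-day SAE endpoint and the 30-day adverse event period. If reduction stops at about Day 0, it also roughly matches adverse event collection to 30 days after return to full immunosuppression. Exposure to reduced immunosuppression would then be about five days plus the PCR turnaround, against the planned five days plus two weeks. This is fair for adverse events. It does not cover the 60-day endpoints, the Month 3 DSA or six-month SAEs.

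Third, the footnote may act as a late eligibility check, with the dose withheld. If so, the windows counted from the vaccine never start. The documents do not settle this, which is why the point is limited to those vaccinated. It should not be inferred that every swab-positive participant is dosed before the result is known.

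Fourth, Appendix 3 can be read as ending only the reduction, with Sections 11.1 and 12.4.1 still in force. Truncation in the reduction arm is therefore the plainer reading but not certain. That ambiguity is itself a reason to edit.

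Finally, a reader might infer that the primary endpoint titre is lost, because the Roche assay is not named among the items kept. That is an inference from silence. The list need not be exhaustive, only mechanistic blood is stopped, and the documents do not say that the primary assay counts as such. How a participant with incomplete 60-day status enters the Fisher test (Sections 13.4.1 and 13.4.3) is also open, but that arises for any early dropout.

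**Conclusion.** The point holds in a limited form. As written, footnote 7 restricts randomised swab-positive participants to Day 30. For those vaccinated, it leaves half of the rejection, graft-loss and death windows unobserved and drops the Month 3 DSA in kidney recipients. It conflicts with Sections 11.1 and 12.4.1, sits poorly with the safeguard in Section 5.3, and is worded differently in the two arms.

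The effect on results is probably very small: about 0.01-0.07 unseen events in all, assuming 1-5% positivity and events spread evenly over a year. The case for change rests on complete and equal safety ascertainment in people already exposed to the intervention, at low cost. Loss of the Week 4 titre is not established. Even if it occurred, at the same positivity it would cost 0.4-2.0 points of power.

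**What to change.** Use the same wording in footnote 7 of both appendices, and separate stopping the intervention from stopping follow-up:

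1. Stop IS reduction (where applicable) and mechanistic blood, as now.
2. Keep vaccinated swab-positive participants, and reduction-arm participants who have started IS reduction, on the scheduled safety visits. Cover rejection, graft loss and death to at least Day 60, the Month 3 DSA in kidney recipients, and SAEs to six months as in Section 12.4.1. Count from the Day 0 visit where no vaccine was given.
3. For follow-up beyond six months, either apply Section 11.1 or write the exception into it.
4. State whether the vaccine is held for the PCR result, and whether the Week 4 Roche titre is drawn. How infection-affected titres enter the primary analysis is the sponsor's choice, to be written down in advance.

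The cost is a wording change in two footnotes and up to four already scheduled visits per person (Weeks 5 and 6, Months 3 and 6). That is 4 x 4 = 16 to 20 x 4 = 80 visits at the assumed positivity. Study contacts may be remote (footnote 3), although laboratory draws still need a sample. Add one Month 3 DSA tube per affected kidney recipient.
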